11.1 Determination of Sample Size

This is a single-arm, open-label phase II study to observe the objective response rate (ORR) and survival rate at 6 months simultaneously.

Referring to the study results on similar products, assuming the ORR is 15% for SHR-1210 in treatment of target population of this study, and the lower limit of 95% confidential interval of ORR obtained from this study is >7%, it can be considered as effective. 154 subjects need to be enrolled to obtain 90% power at a one-sided significance level of 0.025. Further assuming evaluable cases accounting for 80% of the enrolled subjects, 194 subjects are required to be enrolled.

Assuming the survival rate at 6 months is 80% for SHR-1210 in treatment of target population, and the lower limit of 95% confidential interval is >70%, this therapy can be considered to have advantage in efficacy. 200 subjects need to be enrolled to obtain 90% power at a one-sided significance level of 0.025. Considering the drop-out rate of 10%, a total of 220 subjects are required to be enrolled.

Therefore, the planned sample size of this study is 220.

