3. STATISTICAL HYPOTHESIS

All analyses will be primarily based on descriptive statistical summary by group and overall. No formal statistical hypothesis testing will be performed. The overall 95% CIs of the two primary study endpoints, ORR and 6-month OS rate, will be calculated. The lower limit of the overall 95% CI of ORR is > 7% and the lower limit of the overall 95% CI of 6-month OS rate is >70% indicate that the drug is effective.

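### The 6-month OS sample size does not add up: 200 needed, 10% drop-out and 220 enrolled cannot all hold, although the effect on power is minor

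*Protocol*

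**What the plan says.** Protocol 11.1 sizes the trial separately for its two primary endpoints and takes the larger result.

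- **6-month OS rate.** The assumed rate is 80% ("Assuming the survival rate at 6 months is 80% for SHR-1210 in treatment of target population") and the criterion is that "the lower limit of 95% confidential interval is >70%, this therapy can be considered to have advantage in efficacy". From this, "200 subjects need to be enrolled to obtain 90% power at a one-sided significance level of 0.025". The allowance for losses follows: "Considering the drop-out rate of 10%, a total of 220 subjects are required to be enrolled".
- **ORR.** The base size is 154 ("154 subjects need to be enrolled to obtain 90% power at a one-sided significance level of 0.025"), and then: "Further assuming evaluable cases accounting for 80% of the enrolled subjects, 194 subjects are required to be enrolled".
- **Final size.** "Therefore, the planned sample size of this study is 220".

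The synopsis and SAP 2.3 repeat these figures. No inflation formula is written for either endpoint. SAP 3 applies the OS criterion to both dose groups together: "the lower limit of the overall 95% CI of 6-month OS rate is >70% indicate that the drug is effective".

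On the analysis, Protocol 11.2 and SAP 5.1.1 define the FAS as randomized subjects with at least one dose, and the protocol makes it the primary efficacy set. Protocol 11.3.2 and SAP 4.1.7 and 5.4 estimate the 6-month OS rate by Kaplan-Meier. SAP 4.1.6 censors a subject without a recorded death at the last date known alive.

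**The concern.** A drop-out allowance should make the number left after losses equal the number the power calculation needs. Here it falls two short. The base size seems to have been increased by 10% of itself, when a 10% drop-out rate applies to the subjects enrolled.

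The OS calculation gives the larger total (220 against 194), so this step sets the governing sample size in the protocol, synopsis and SAP. What is at stake is mainly whether the stated justification is correct. A reader can disprove it with one multiplication. It also has to be checked whether the slip damages the power claimed for a primary endpoint.

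**Working it through.** **Inputs (Protocol 11.1).** OS: p1 = 0.80, p0 = 0.70, one-sided level 0.025, power 90%, base size 200, drop-out 10%, enrolled 220. ORR: base size 154, evaluable share 80%, enrolled 194.

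**Step 1: reproduce the base size of 200.**
- Normal approximation: n = [(1.960 × √(0.70 × 0.30) + 1.282 × √(0.80 × 0.20)) / 0.10]² = 199.03, rounded up to 200.
- Exact binomial, requiring a Clopper-Pearson lower limit above 70%: the smallest n with at least 90% power is 200 (153 or more survivors, power 90.6%, one-sided error 0.0249).

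The 200 is sound.

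**Step 2: the inflation.**
- 200 × 1.10 = 220, exactly the stated figure.
- 220 × 0.90 = 198 retained, 2 below 200.
- 200 / 0.90 = 222.2, rounded up to 223. Then 223 × 0.90 = 200.7 retained.
- Allowance actually provided by 220: (220 − 200) / 220 = 20/220 = 9.1%.

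The shortfall is 3 enrolled subjects, 3/223 = 1.3%.

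**Step 3: the ORR inflation in the same section.**
- Division: 154 / 0.80 = 192.5, rounded up to 193.
- Multiplication: 154 × 1.20 = 184.8, rounded up to 185.
- Stated: 194.

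Division is far closer. Rounding 192.5 up to an even number for 1:1 allocation would give 194, but the plan does not say this was done.

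**Step 4: power if drop-outs are discarded (complete-case).** The normal formula is power = Φ[(0.10√n − 1.960 × √0.21) / √0.16].
- n = 198: Φ(1.272) = 89.8%.
- n = 200: Φ(1.290) = 90.1%.

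Exact power for the rule that the Clopper-Pearson lower limit exceeds 70%, when the true rate is 80%:

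| n | survivors needed | power |
|---|---|---|
| 197 | 151 | 89.5% |
| 198 | 152 | 88.8% |
| 199 | 153 | 88.1% |
| 200 | 153 | 90.6% |
| 201 | 154 | 89.9% |
| 202 | 155 | 89.3% |
| 203 | 156 | 88.6% |

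Exact power moves in a sawtooth: 203 subjects give less power than 198. The 1.7-point gap between 198 and 200 is therefore mostly discreteness. The smooth difference is 0.3 points.

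**Step 5: power under the planned analysis.** Kaplan-Meier estimate at month 6 with 220 subjects, by simulation (20,000 runs). Assumptions, not from the documents: exponential survival with 80% alive at 6 months; 10% drop-out by month 6, unrelated to prognosis, spread either uniformly or exponentially over the period. The SAP does not name the form of the Kaplan-Meier interval, so two were tried.
- Log-log interval: about 90% to 91%.
- Linear interval: about 93%.

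With exponential drop-out, 223 subjects gave essentially the same power as 220.

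**The case against.** The strongest reply is that 198 is not the number that enters the planned analysis. The primary set is everyone randomized and dosed, and Protocol 3.2.2 requires the first dose within 3 days of randomization, so few should be lost before entering the FAS. A dosed subject who later drops out is censored and contributes follow-up until then. Protocol 3.1 also treats 220 as approximate, and a gap of 3 lies within that wording.

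This stands as regards consequence. A reader might infer from 198 against 200 that the trial cannot deliver its 90% power. The documents do not support that: the reading requires drop-outs to be thrown away, and step 5 shows power of about 90% or more when they are censored as planned. Protocol 8.1 does define the 6-month rate as a proportion among evaluable subjects, which is not the Kaplan-Meier estimate of the SAP. But evaluable there means at least one dose and one later tumor assessment, not completion of 6 months, so it does not establish a 10% loss either.

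A reader might also take it as established that two inflation rules were used. That is an inference from how well the figures fit. No formula is given, and plain division gives 193 for ORR, not 194.

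The reply does not repair the sentence. A drop-out allowance treats drop-outs as lost, and on that footing 200, 10% and 220 contradict each other whichever rule was used.

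**Conclusion.** The sample-size statement for 6-month OS is arithmetically wrong as written, in three places, and it sets the governing sample size. The error is 2 retained or 3 enrolled subjects. Its power cost in the worst case, with all drop-outs discarded, is 0.3 points by the normal approximation and 1.7 points exactly. Under the planned analysis, power with 220 remains about 90% to 93%, given the survival and drop-out assumptions in step 5. The trial is not materially underpowered and the effectiveness criterion in SAP 3 is unaffected. Severity: minor.

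**What to change.** In Protocol 11.1, the synopsis and SAP 2.3, restate that enrolling 220 allows for about 9.1% drop-out while retaining 200.

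If 10% is kept, say instead that 198 would remain, giving slightly under 90% power in a complete-case analysis and about 90% or more under the planned Kaplan-Meier analysis of the FAS. The complete-case figure should not stand alone, because it would misdescribe the planned analysis. It would also help to write out the inflation rule, dividing by the retained share, for both endpoints.

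The cost is one sentence in three places and a slightly less favourable stated drop-out allowance. Enrolment, analysis and decision criterion do not change.

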11.2 Analysis Populations

Full analysis set (FAS): an analysis set determined in accordance with intention-to-treat principle. All the subjects who are randomized and have documented at least one dose of investigational drug will be included in this analysis set. The full analysis set is the primary efficacy analysis set.

Per protocol set (PPS): one subset of full analysis set. The subjects with protocol violation which has important influence on efficacy will be excluded from this set. The list of subjects who are included or excluded from PPS needs to be determined through review by the sponsor and investigators prior to lock of database.

Safety analysis set (SS): all the subjects who are randomized and have documented at least one dose of investigational drug will be included in the safety analysis set.

PD-L1 analysis set: PD-L1 expression analysis set of this trial comprise of all the subjects who have been randomized and enrolled and have received at least one dose of the investigational drug, and have provided tumor biopsy samples.

11.3 Statistical Analysis

11.3.1 General analysis

Unless otherwise specified, the continuous variables in this study will be summarized with mean, standard deviation, median, maximum and minimum; the categorical variables will be summarized with frequency and percentage; Kaplan-Meier method will be used to estimate the survival rate and plot survival curve for time-event data.

11.3.2 Efficacy analysis

The tumor evaluation will be performed by the investigators based on RECIST v1.1. This evaluation data will be based on following responding parameters: complete response (CR), partial response (PR), stable disease (SD), progression of disease (PD), and not evaluable (NE). All the efficacy analysis will be based on the full-analysis set.

The survival distribution of OS will be estimated based on Kaplan-Meier (KM) method, median OS and two-sided 95% confidential interval will be calculated. In addition, KM method will be used to estimate the probability of survival at different time points (at month 6/9/12), and the corresponding 95% confidential interval will be calculated. Moreover, the subgroup analysis of OS will be performed by the predefined factors, the analytical method will be based on the aforementioned method.

The survival distribution of time to progression (TTP) will be estimated based on Kaplan-Meier (KM) method, median TTP and two-sided 95% confidential interval will be calculated.

The survival distribution of progression-free survival (PFS) will be estimated based on Kaplan-Meier (KM) method, median PFS and two-sided 95% confidential interval will be calculated. Objective response rate (ORR) and disease control rate (DCR): Clopper-Pearson method will be used to calculate the 95% confidential interval of overall percentage.

11.3.3 Safety analysis

Analysis of adverse events will be based on the safety analysis set. The data for analysis will include but not limited to the calculation of the incidence of adverse reactions by group; incidences and frequencies of adverse reactions by system; calculation of the percentage and detailed listing of a variety of adverse events, and the specific analysis will be presented in the statistical analysis plan.

Number of “normal to abnormal” or “exacerbation of abnormal” laboratory parameters, ECG, physical examinations and the abnormality conversion rate after the trial, the number of abnormal laboratory parameters, ECG, physical examinations and the clinical explanation would be presented.

11.3.4 Exploratory analyses

PD-L1 expression will be analyzed using descriptive statistics. PD-L1 analysis set is the analysis data set.

12 INFORMED CONSENT AND ETHICS

12.1 Informed Consent

The clinical research physician must fulfill the obligation of full disclosure to the subjects, and explain to subjects that they are voluntary to participate in the clinical trial, and have the right to withdraw from the trial without discrimination and retaliation at any time during the trial, their medical treatment and benefits would not be affected at all and they could still continue other treatment. The subjects must be made aware that the participation in the trial and the personal data in the trial are kept confidential. The property, objective, expected possible benefit and possible risks and inconvenience of the trial are also needed to be informed to the subjects, the available other therapies, rights and obligations for subjects in compliance with the Helsinki Declaration should be informed to the subjects, allowing subjects to have adequate time to consider whether they are willing to participate in the trial and sign the informed consent form.

12.2 Ethical Principles

This trial protocol needs to be approved by the hospital ethics committee prior to its conduct with written approval. The study protocol, amendments, informed consent form and other relevant documents, e.g., recruitment advertisement, should be provided to the ethics committee. This study shall be conducted strictly in accordance with the Declaration of Helsinki and Good Clinical Practice (GCP) and relevant regulations issued by NMPA. Prior to the start of the trial, the approval from the ethics committee must be obtained, the study could be initiated then.

The sponsor and investigator must not amend this study protocol unilaterally without mutual agreement. Only limited to eliminate the direct and immediate injury to subjects, investigators can change or deviate from the study protocol prior to approval by the ethics committee/institutional review board. At the same time, all the deviations or changes made, their reasons, and the recommended amendment to the protocol should be submitted to the ethics committee/institutional review board for review as soon as possible, and communicate with the sponsor. Investigators must explain and record any deviation from the protocol.

During the clinical study, any amendment made to the study protocol should be submitted to the ethics committee, corresponding amendment should also be made to other study documents when necessary and submitted and/or approved as required by the ethics committee. Investigators are responsible for periodic submission of the in-trial report to the ethics committee in accordance with relevant requirement, and should inform the ethics committee that the trial has ended after the end of trial.

12.3 Regulatory Considerations

SHR-1210 for injection, innovatively developed and submitted for approval by Jiangsu Hengrui Pharmaceuticals Co., Ltd., has been approved by NMPA, and given the clinical trial approval for national Class I new drugs. Now, the nationwide, multi-center, phase II/III clinical trial on SHR-1210 for injection in the subjects with advanced hepatocellular carcinoma who had received systematic treatment previously is conducted in accordance with Drug Registration Regulation and GCP, led and organized by National Drug Clinical Research Institute of the 81st Hospital of PLA (Nanjing).

12.4 Security Measures of Subject Information

Every effort will be made to protect subject's personal privacy during the study. Subject's name and other personal privacy information must not be included in the study related documents, study report, publications and any other public materials, unless required by the law. Collection, transmission, process and maintenance of subject's information will be in accordance with the provisions in relevant laws and regulations, so as to protect subject's personal data from disclosure.

13 QUALITY CONTROL AND QUALITY ASSURANCE

- The clinical trial institution must be the base of drug clinical trials determined by NMPA with clinical study conditions;
- The study staff must be the qualified persons who have been trained on clinical trials, and conduct their work under the guidance of highly specialized personnel.

- The clinical ward must be in accordance with the standardized requirement before the trial, so as to ensure complete rescue equipment;
- The dose will be given by healthcare professionals, intake of the drug will be carefully understood, so as to ensure subject's compliance;
- Each study center must conduct it strictly in accordance with the study protocol and fill in the eCRF truthfully;
- The monitor should follow the standard operating procedure to supervise the conduct of the clinical trial, confirm proper and complete record and report of all the data, accurate filling of all the eCRFs and consistency with the original data, and ensure the trial is conducted in accordance with the protocol;
- Once SAE occurs, the sponsor must inform each study unit promptly, the study needs to be discontinued temporarily if necessary;
- Each center participating in the trial should receive the audit from the sponsor and Food and Drug Administrations, it is particularly important for the investigators and relevant staff to provide convenience and time for the monitoring and audit.

14 PUBLICATION OF STUDY RESULTS

Hengrui does not restrict the investigators to publish any information collected or produced, despite whether this result favors for the investigational drug. However, in order to make sure no unintentional leakage of the confidential information or unprotected invention, the investigators must give an opportunity for sponsor to review any proposed publication or publication in other forms in advance prior to submission or publication of the documents. If the study is one part of one multi-center study, the investigators need to agree on the first publication of the comprehensive results from all the study centers. However, if the manuscript of the comprehensive analysis has not been submitted for publication within 12 months after completion or termination of the study at all the study sites, investigators can request independent publication of the results in accordance with other requirement in this section.

15 SCHEDULE OF THE TRIAL

Expected Oct. 2016 to May 2018 (primary endpoint analysis)

16 PROTOCOL COMPLIANCE

Investigators will guarantee that every effort will be made to avoid violations from the protocol. Investigators cannot contact with Jiangsu Hengrui Pharmaceuticals Co., Ltd. to request approval of the violation from the protocol at any time, as no any authorized violation of the protocol shall

be allowed. If investigators consider some deviation from the protocol can improve the implementation of the trial, amendment to the protocol must be considered, however, it can be conducted only when the amendment is agreed by Jiangsu Hengrui Pharmaceuticals Co., Ltd. and approved by the medical ethics committee. All the major violations from the protocol will be recorded and reported on the clinical trial report.

Annex 1 Response Evaluation Criteria in Solid Tumors RECIST Version 1.1

1 Measurability of Tumor at Baseline Level

1.1 Definition

At baseline level, tumor lesions/lymph nodes can be divided as measurable and non-measurable according to the definitions below:

Measurable Lesions

Tumor lesions: at least one diameter that could be precisely measured (recorded as maximum diameter), its minimum length is as below:

- 10 mm for CT scan (thickness of CT scan is no more than 5 mm)
- 10 mm for clinical routine instrument (tumor lesion that could not be accurately measured by diameter-measuring instrument should be recorded as non-measurable)
- 20 mm for chest X-ray
- Malignant lymph nodes: pathologically enlarged and measurable, and short axis ≥ 15 mm for single lymph node in CT scan (thickness of CT scan recommended no more than 5 mm). Only the short axis is measured and followed up at baseline and during follow-up.

Non-measurable Lesions

All the other lesions, including small lesions (maximum diameter < 10 mm or short axis of pathological lymph node ≥ 10 mm and < 15 mm) and non-measurable lesions. Non-measurable lesions include: meningeal disease, ascites, pleural or pericardial effusion, inflammatory breast cancer, skin/pulmonary cancerous lymphatic inflammation, abdominal mass that cannot be diagnosed and followed up by radiology, as well as cystic lesion.

Special Considerations on the Measurement of Lesions

Osseous lesion, cystic lesion and the lesion previously given topical therapy needed to be specially noted:

Osseous lesion:

- Bone scan, PET scan or plain X-ray are inappropriate for measurement of osseous lesions, however, they can be used for confirmation of the presence or disappearance of osseous lesions;
- If the osteolytic lesion or mixed osteolytic/osteogenic lesion with determined soft tissue component could be evaluated with tomographic imaging technique, such as CT or MRI, when the soft tissue component meets the above definition on measurability, these lesions can be regarded as measurable lesion;

- Osteoblastic lesions belong to non-measurable lesions.

Cystic lesions:

- The lesions meeting the definition of radiologically simple cyst should not be considered as malignant foci as they are simple cysts in terms of the definition; they are neither measurable lesions nor the non-measurable lesions.
- Cystic metastatic lesions that meet the above definition on measurability can be considered as measurable lesions. However, if non-cystic lesions are present in the same patient, the non-cystic lesions should be preferably selected as the target lesion.

Lesions treated topically:

- The lesions located at the site once radiated or treated with other topical therapies are generally considered as non-measurable lesions, unless clear progression occurred in these lesions. The study protocol should describe the conditions for these lesions to become measurable lesions in detail.

1.2 Description of Measurement Method

Measurement of Lesions

Measurement of all the tumors is recorded in meter in the clinical evaluation. All the baseline evaluations in terms of the size of tumor foci should be completed as close as possible to the start of treatment, and must be completed within 28 days (4 weeks) prior to the start of treatment.

Methods of Evaluation

Baseline evaluation and subsequent measurements of a lesion should be carried out by the same techniques and methods. All the lesions must be radiologically evaluated except those that cannot be radiologically evaluated but only be evaluated with clinical examinations.

Clinical lesion: only the superficial clinical lesions with diameter ≥ 10 mm measured could be considered as measurable lesions (e.g., cutaneous nodule). For patients with cutaneous lesions, it is advised to use the color image containing one ruler to measure the size of lesion for documentation. When the lesion is evaluated with radiology and clinical examination simultaneously, the radiological evaluation should be used as much as possible as it is more objective and can be reviewed repeatedly at the end of the study.

Chest X-ray: when the progression of tumor is used as the important endpoint, chest CT should be used preferably, as it is more sensitive than X-ray, in particular for new lesions. Breast X-ray are only suitable when the lesion measured has a clear border and pulmonary ventilation is patent.

CT, MRI: CT is currently the best reproducible method for evaluation of efficacy. The definition of measurability in this guideline is based on the thickness of CT scan ≤ 5 mm. If the thickness of CT scan is more than 5 mm, the measurable lesion should be at least 2 times of the thickness. MRI could also be accepted in some circumstances (e.g., systemic scan).

Ultrasound: ultrasound should not be used as one method for measurement of the size of lesion. Ultrasonography is not reproducible due to its dependency on the operation, thus could not ensure the technical and measurement consistency between different measurements. If one new lesion is found in ultrasound during the trial, CT or MRI should be used for confirmation. If the exposure to the radiation from CT scan is considered, alternative MRI can be used.

Endoscopic and laparoscopic examination: these techniques are not recommended for the objective evaluation of tumors, however, these methods can be used for confirmation of CR when biopsy specimen is obtained, and for confirmation of recurrence in the trial while recurrence after CR or surgical resection are taken as the study endpoint.

Tumor marker: tumor marker cannot be used independently to evaluate the objective response of tumors. However, if the marker level exceeds the upper limit of normal at baseline, it must return to the normal level when it is used to evaluate complete response. As the tumor marker varies for disease, it is needed to be considered when including this measurement criterion in the protocol. The specific criteria on CA-125 response (recurrent ovarian cancer) and PSA response (recurrent prostate cancer) have been published. The criteria on CA-125 progression have been established by the international organization of gynecological cancers, i.e., it will be added in the evaluation criteria on the objective response of tumors in the 1st-line therapy for ovarian cancer.

Cytological /histological technology: in the specific situations specified in the protocol, these techniques can be used to differentiate PR and CR (e.g., residual benign tumor tissue is usually present in the lesions of germline cell tumors). When exudation is possibly one potential side effect of one therapy (e.g., Taxanes or angiogenesis inhibitor), and the measurable lesion met the criteria on response or stable disease; cytological technique could be used to differentiate response (or stable disease) and progression of disease when tumor related exudation occurred or became exacerbated during the treatment.

2 Tumor Response Evaluation

